## 2.5 Rationale

In patients with DM1 and severe gastrointestinal neuropathy, FMT could potentially change the composition of bacteria in the gut and reduce symptoms without the use of antibiotics. However, the use of FMT may have potentially serious side effects in patients with reduced gastric emptying, prolonged transit time through the small intestine, increased permeability of the gut and reduced resistance to infections. To date, no studies investigated the effects of FMT in patients with DM1 and severe gastrointestinal neuropathy. Therefore, it is necessary to evaluate the safety and pilot efficacy in a small group of patients before designing a large trial.

If this method is both acceptable, safe, and effective, it may provide a simple and antibioticfree way of treating gastrointestinal symptoms in DM1 in an out-patient setting. This study will provide data on safety, tolerability and pilot efficacy which is an absolute necessity for further research within the field.

## 2.6 Background

### 2.6.1 Severe gastrointestinal neuropathy in diabetes mellitus

DM1 is strongly associated with diarrhea, nausea, vomiting, abdominal pain, bloating, constipation and faecal incontinence(1, 2). Though the severity of symptoms varies, severe cases suffer from daily uncontrollable diarrhea, vomiting, intense nausea, and faecal incontinence with severe consequences for social activities and quality of life(3). Additionally, nightly uncontrolled bowel movements pose a clinical challenge.

Earlier studies of patients with DM1 have demonstrated demyelination, axonal damage and reduced number of motor fibers in vagal nerves(4-6). Other studies report degeneration of nerve fibers within the enteric nervous system, including the Cajal cells (the pacemaker cell of the bowel)(7, 8). Today, it is assumed that diabetic gastrointestinal (GI) dysfunction is caused by autonomic neuropathy, dysfunction of the Cajal cells, and reduced contractility of the intestinal smooth muscle cells(7-9). The clinical effect of each component remains unknown.

### 2.6.2 Intestinal microbiota in diabetes mellitus type 1

Several studies have compared the gut microbiota of patients with early DM1 or even at a prediabetic stage with those of healthy volunteers. Findings have not been conclusive, but most have found reduced diversity of the intestinal bacterial community and increased proportion of *Bacteroides*(10). Preclinical studies support the hypothesis that specific features of the microbiota give rise to impaired intestinal permeability(11), which further influence T cell autoimmunity and B-lymphocytes.

This may lead to beta-cell destruction and DM1. However, most research on gut microbiota and DM has been in DM type 2. Thus, the impact of the microbiota in humans with DM1 and GI symptoms remains obscure

#### 2.6.3 Abnormal gut microbiota and gastrointestinal dysfunction in diabetes

The pH within the colon is lower than in the small intestine. This is mainly because of fermentation of bacteria in the right colon. Recently, we have shown that the pH drop from the small intestine to the colon is larger in patients with DM1 and neuropathy than in healthy individuals(12). This may be a result of increased fermentation caused by an abnormal microbiota. Our partners at the Technical University of Denmark have found that the diversity and composition, as well as the metabolic activity of the colonic microbiota is strongly associated colonic transit time(13).

In a recent study, we found that patients with DM1 and severe GI symptoms accumulate faeces and excessive amounts of gas in the caecum(14). Hence, we speculate that diabetic intestinal neuropathy causes dysmotility and stasis of stools in the right colon, resulting in abnormal microbiota composition and increased gas production. The excessive amounts of gas produced by the bacteria will distend the caecum until it responds with a forceful contraction causing explosive bowel moments resulting in diarrhea. Moreover, the increased gas production will contribute to the severe abdominal bloating and pain commonly reported by patients with DM1.

In clinical practice, most patients with DM1 and severe GI neuropathy have prolonged or normal transit time through the colon. Hence, standard treatment with constipating agents aggravates other bowel symptoms, especially symptoms caused by gastroparesis. The only treatment with a reasonable degree of success is repeated cycles of broad-spectrum antibiotics aimed to reduce bacterial overgrowth. Unfortunately, the effect is temporary and complications are common.

#### 2.6.4 Faecal microbiota transplantation in patients with diabetes mellitus type 1

FMT is a method used to induce permanent changes of the gut microbiota. The microbiota from minimally processed faeces, containing whole microbial communities from a healthy donor, is transferred to a recipient and drives a prompt engraftment of a donor-like microbiota in the recipient(15). FMT is an established and efficient treatment to recurrent infections with *Clostridioides difficile* infection (CDI) with cure rates above 90 %(16-19). Most of our knowledge about the safety of FMT relies on studies with patients with recurrent CDI, and these studies often include patients with a high age and comorbidity. Even in these patients, FMT is well tolerated(20).

The Center for Faecal Microbiota Transplantation (CEFTA) at AUH is among the foremost internationally within the clinical use of FMT(21, 22). Recently, we developed FMT capsules for oral intake. This application method is simple, with low risk and is able to induce longterm changes in the microbiota(23). In patients with DM1, this may potentially reduce diarrhea, bloating and pain, without massive use of antibiotics. Simple and appealing as it may seem, the use of FMT may have unwanted consequences in patients with DM1. Reduced gastric emptying, prolonged transit through the small intestine, increased permeability of the gut and reduced resistance to infections could potentially predispose to serious side effects of FMT.

To the best of our knowledge, no studies of FMT in patients with DM1 and severe bowel dysfunction have been performed. It would therefore be unethical to introduce treatment or to conduct large trials without first ensuring the safety and tolerability in a small group of patients. Furthermore, the design of a regular and sufficiently powered trial requires pilot data on the efficacy of treatment and information on whether a single dose is sufficient to cause changes in the gut microbiota. Based on the above considerations, we believe that FMT holds great promise in DM1 enteropathy, but a thorough study providing data on safety, tolerability and pilot efficacy is an absolute necessity for further research within the field.

## 2.7 Previous study

Interest in FMT to treat disease has risen over the last few years and its therapeutic benefit is currently being explored for a variety of diseases. Numerous studies have explored the link between gut microbiota and DM1. However, there are no published studies investigating the safety of FMT against severe GI neuropathy in patients with DM1. Use of MeSH-band search is limited because FMT was first defined as a MeSH term in 2016. A PubMed search [2th October 2020] showed no previous study on the subject using the following search string:

[(((diabetes) OR diabetes type 1)) AND (((((faecal microbiota transplantation) OR fecal microbiota transplantation) OR faeces transplantation) OR human intestinal microbiota transfer) OR faecal bacteriotherapy)].

# 3.0 Methods and their justification

## 3.1 Study design

The study is a 8-week, randomised, double-blinded, placebo-controlled pilot trial of oral FMT versus placebo in patients with DM1 and severe GI neuropathy. The intervention period consists of a first 4 weeks where patients receive either FMT or placebo and a second 4 weeks where all patients receive FMT (Figure 1 and 2). The patients will undergo the investigations before and after each 4-week period. When the patients have completed the study period, they will be contacted by telephone every second month for two years. They will be asked about their gastrointestinal symptoms. The patients will be offered further treatment with FMT, if they experience relapse of symptoms and a score of or above 40 in the GSRS-IBS questionnaire.

The design is chosen to allow the evaluation of the safety and tolerability of FMT in patients with DM1. We will also be able to evaluate if FMT is superior to placebo, how it affects the intestinal microbiota and if the effects of two doses of oral FMT is superior to one dose.

## 3.2 Intervention

### 3.2.1 Faecal microbiota transplantation

FMT may be administered via the upper route, using capsules or a nasojejunal tube, or via the lower route using colonoscopy. Oral administration with covered capsules is a patient-friendly and safe administration form, and it requires no specific patient preparation. At CEFTA, donor faeces is obtained from thoroughly screened healthy blood donors and processed in compliance

with the European Tissue and Cells Directive(21, 22). The faeces is minimally processed through a series of centrifugation steps and dispensed into double-coated, acid resistant enterocapsules (VcapsTM size 0 and 00, Capsugel®). A single treatment includes approximately 22 capsules ( $\sim$ 50 grams of original donor faeces) each sized 0.5 x 2 cm. The capsule coating has a smooth surface making them easy to swallow. We have successfully applied FMT capsules in more than 200 patients with recurrent *Clostridioides difficile* infection, the main indication of FMT, with success rates comparable to other administration forms by naso-jejunal tube or colonoscopy(16) If a patient has completed the first two treatments with FMT capsules, and meets the criteria for further treatment, and the patient has had difficulty swallowing the capsules or have vomited during or after treatment with FMT, the patient may be offered treatment by colonoscopy or nasojejunal tube.

### 3.2.1.1 Clinical application of FMT

Clinical treatment takes place in the Department of Hepatology and Gastroenterology and will be administrated according to National clinical guidelines(24) and the described standard protocol (FMT ud-af-huset-vejledning, appendix 1). Prior to clinical treatment, the FMT is released and dispensed from the freezer of the CEFTA laboratory according to a standardised release protocol compliant with safety standards for handling blood components. Safety samples are taken from all FMT treatments, and the samples are saved for later traceability and testing.

All patients arrive fasting (6 hours) for their randomised dedicated treatment. Treatment with capsule-FMT or capsule-placebo takes place in outpatient observation rooms. Prior to treatment, patients receive a single dose of peristaltic 10 mg tablet metoclopramide. The physician responsible for the treatment breaks the seal and the capsules with FMT or placebo are indigested with diet soda over 10-30 minutes. Outpatients then leave the ward to their own home.

### 3.3 Analyses

#### 3.3.1 Assessment of gastrointestinal symptoms

a) Patients will fill in a daily bowel diary, commonly used at our unit and a side effect schedule which will be handed out to the patients in paper form. The patients will fill out the diary and side effect schedule for one-week diary four times: at baseline, during the first week of each intervention period, and at longterm follow-up after 26 weeks. The diary contains questions that include number of daily bowel movements, consistency of stools (Bristol stool chart), time spent at defecation, nightly bowel movements, episodes of faecal incontinence, days with abdominal bloating/pain and the amount of insulin used. The side effect schedule will contain a schedule of commonly known side effects and an assessment of the severity of the side effect (appendix 2).

The following four questionnaires will be filled out by the patient on an Ipad during the scheduled visits and the data will be saved directly in REDCcap.

- b) GSRS-IBS: The Gastrointestinal syndrome rating scale irritable bowel syndrome version (GSRS-IBS) is a 13-item questionnaire developed and validated for irritable bowel syndrome(25). The items cover some of the most common bowel symptoms experienced by patients with DM1. These include pain, bloating, diarrhea, constipation and gas. The questionnaire adds to a total score which covers the previous week. The questionnaire has been developed and validated in a Nordic country (Sweden), translated into Danish and subsequently used in several studies from our unit at AUH (appendix 3).
- c) PAGI-SYM: The patient assessment of upper gastrointestinal symptom severity index (PAGI-SYM) questionnaire has been developed and validated for functional dyspepsia(26). The questionnaire is composed of 20 items with 6 subscales: heartburn/regurgitation, nausea/voliting, fullness/satiety, bloating, upper abdominal pain and lower abdominal pain. PAGI-SYM scores have been shown to correlate with gastric emptying rate and gastric hypersensitivity and therefore may be useful in the evaluation of gastroprokinetics(26) (appendix 4).
- d) IBS-IS: The irritable bowel syndrome impact scale (IBS-IS) is a 26-item questionnaire developed to capture the impact of irritable bowel syndrome and its treatment on patients' lives(27). The 26-items represent five domains: Fatigue. Impact on daily activities, sleep disturbance, emotional distress and eating habits (appendix 5).
- e) COMPASS-31 is a 31-item questionnaire for assessing symptoms of dysautonomia. The questionnaire has been validated in patients with small fiber polyneuropathy(28). It quantifies 6 domains: orthostatic intolerance, vasomotor, secretomotor, gastrointestinal, bladder and pupillomotor (appendix 6).

#### 3.3.2 Wireless Motility Capsule

The Wireless Motility Capsule (WMC) consists of an indigestible capsule that continuously measures pressure, temperature and pH as it traverses the GI tract(29). Based on stereotypical landmarks, gastric emptying time, small bowel transit, colonic transit time and whole gut transit time can be delineated in a single recording (Figure 3). Data is transmitted wirelessly to a receiver unit worn by the patient until the capsule is expelled. Investigations on normal values have been performed and the WMC is CE marked and its use has been approved by the US Food and Drug Administration as well as the European Authorities. In a study among patients with DM1 experiencing GI symptoms, 65% had prolonged gastric emptying, 24% had prolonged small intestinal transit and 58% had prolonged colon transit time(29).

In the present study, assessment with the WMC will serve to classify patients into those with normal or prolonged gastric emptying/small intestinal transit at baseline. Further, the method will quantify changes in the pH of the colon (a marker of fermentation) from baseline to after FMT. Finally, the WMC will provide a direct measure of colonic transit time at baseline and after intervention with FMT. The WMC is available at our centers.

#### 3.3.2.1 System malfunction

There has only been reported a small number of cases of system malfunction. These included inabilities of the patient to swallow the capsule, failure of the capsule to record or to transmit data, failure of the receiver to record or download data and software malfunctioning.

In a clinical trial with 495 subjects receiving WMC involving healthy, gastroparetic and constipated patients, 3 patients were unable to swallow the capsule, yielding a failure-to-swallow incidence rate of 0,6%. In the same clinical trial there were 36 (7,2%) incidences of equipment or software malfunctioning preventing the acquisition of interpretable transit data from the WMC(30). The trial involved prototypic equipment that has since been upgraded. In a postmarketing analysis of approximately 5,000 WMC ingestions, the incidence of equipment failure was reported to be 0.8-0.9%(31).

#### 3.3.3 Low-dose abdominal CT scan

A low-dose high-resolution CT scan will be performed after a minimum of 6 hours fasting for food and a minimum of 2 hours for liquids. The scan field covers an area from at the left cardiac ventricle to the lower part of the anal canal allowing assessment of abdominal organ volumes as well as gas and fluid volumes within the gut. Data analysis will be performed in PMOD version 3.6 (PMOD Technologies, Zurich, Switzerland). Regions of interest are manually defined on each slice of the CT. Volumes-of-interest are computed by fusing all the regions of interest. Water/fluid is defined by Hounsfield CT unit < 30 for water and < -200 Hounsfield units for gas. The investigator making all analyses will be blinded to the clinical category of the test subject and whether the scan is performed at baseline or after intervention with FMT.

### 3.3.4 Breath tests

Due to the acidity of the stomach and the distally propagating small intestinal motility, the concentration of bacteria in the small intestine is low. This is in strong contrast to the colon where the concentration is extremely high. Increased numbers of bacteria in the small intestine may cause bloating, malabsorption and diarrhea. A simple diagnostic test for small intestinal bacterial overgrowth is the breath test whereby a substrate (80 g glucose dissolved in 300 ml of water) is swallowed. When the glucose gets into contact with bacteria, it is fermented and gas is produced, absorbed and excreted in the breath. The exhaled air is collected in small bags and analysed. An early peak of hydrogen or methane indicates small bacterial overgrowth. The method is simple and non-invasive, but results should be taken with caution because of several sources of error(32).

#### 3.2.6 Stool samples

Stool samples are collected by the patient though the study period. Stool samples are used for both routine diagnostics and research purposes with later microbiome analysis.

### 3.3.6 Blood samples

Blood samples will be taken during the study period. There are indications that the gut microbiota may influence the glycemic control. The exploration of this is beyond the scope of the present study. However, blood glucose and HbA1c levels will be determined during the study.

### 3.3.7 Control of blood glucose before and during the investigations

The patients will be fasting for the investigation with WMC, low-dose CT scan, breath test and for the intervention with either FMT or placebo. The patients will be fasting from midnight the night before the day of investigation. Fasting takes place at home as the diabetic patients are used to monitor their blood glucose. The patients take their morning insulin and refrain from taking other oral medications. Blood glucose is measured once an hour while fasting in the hospital. If the blood glucose during the fasting period or during the study exceeds 10 mmol / l, the following regime with fast-acting insulin will be followed:

Blood glucose 11-12 mmol/l give 4 IU

Blood glucose 12-16 mmol/l give 6 IU

Blood glucose > 16 mmol/l give 8 IU

The interval between supplemental subcutaneous insulin should be 2-4 hours. Alternatively, the insulin can be administered intravenously. If the blood glucose falls below 5 mmol / 1, 500 ml of 10% glucose is given on a side drop 25 ml/h.

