# 11.0 Reimbursement

Participation involves nine visits at AUH. The visits only require that the participants stay at AUH for a few hours at a time. All participants can be reimbursed for documented transport expenses and lost wages after each completed intervention period. Reimbursement for lost wages is considered taxable as B-income.

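### The supplemental-insulin rule in Protocol section 3.3.7 has no row for readings between 10 and 11 mmol/l and two rows for a reading of 12 mmol/l

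*Protocol*

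**What the plan says.** Section 3.3.7 covers the visits at which patients fast: wireless motility capsule, low-dose CT, breath test, and the FMT or placebo intervention. Glucose is checked hourly while the patient fasts in hospital. The trigger applies both to the fasting period and to the study itself: if glucose "exceeds 10 mmol / l, the following regime with fast-acting insulin will be followed". The regime has three rows:

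- "Blood glucose 11-12 mmol/l give 4 IU"
- "Blood glucose 12-16 mmol/l give 6 IU"
- "Blood glucose > 16 mmol/l give 8 IU"

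For a reading below 5 mmol/l, the same section says "500 ml of 10% glucose is given on a side drop 25 ml/h". It gives no duration or stopping point.

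Other sections describe the setting. Section 3.6 keeps participants as outpatients in one department. Section 3.6.3.1 schedules visit 3 from 08.00 to 11.00. Section 3.2.1.1 sends patients home after the capsules. Section 11.0 states "The visits only require that the participants stay at AUH for a few hours at a time". Section 6.1.1 offers admission, where needed, to patients with events or side effects.

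**The concern.** A numeric dosing rule should map each reading that triggers it to exactly one instruction. This one appears to give no instruction just above its trigger and two different instructions at one row boundary. The wording is mandatory once the trigger is passed, so staff who meet either case must improvise and cannot show that they followed the protocol.

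The rule is in routine use. By Table 1 the investigations and interventions it names fall at visits 2 to 8, that is seven visits per patient, or 7 × 20 = 140 planned visits for 20 completers. The patients use insulin, and section 3.3.7 has them take their morning dose while fasting. What is at stake is consistent handling of glucose in a trial whose stated aim includes safety.

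The low-glucose instruction raises a second question: whether the stated volume can be given at the stated rate within a visit.

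**Working it through.** The protocol states no derived figure here, so there is none to reproduce. The check is a direct reading of the rows and one division.

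**Inputs, all from section 3.3.7 unless noted**
- Trigger: above 10 mmol/l.
- Row 1: 11 to 12 mmol/l, 4 IU. Row 2: 12 to 16 mmol/l, 6 IU. Row 3: above 16 mmol/l, 8 IU.
- Low-glucose instruction: below 5 mmol/l, 500 ml of 10% glucose at 25 ml/h.
- Visit 3: 08.00 to 11.00, so 3 h (section 3.6.3.1).

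**Step 1: mapping of readings to rows, one decimal, 10.1 to 18.0 mmol/l**

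| Reading (mmol/l) | Regime triggered? | Rows that apply |
|---|---|---|
| 10.0 | no | none |
| 10.1 to 10.9 | yes | none |
| 11.0 to 11.9 | yes | 4 IU |
| 12.0 | yes | 4 IU and 6 IU |
| 12.1 to 16.0 | yes | 6 IU |
| above 16.0 | yes | 8 IU |

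The gap lies strictly between 10 and 11. The overlap is the single value 12, where the two doses differ by 6 − 4 = 2 IU (6/4 = 1.5). The boundary at 16 is clean.

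**Step 2: the same check in whole numbers**

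The first whole number above 10 is 11, which row 1 covers, so the gap disappears. The reading 12 still falls in two rows. The overlap therefore does not depend on reading precision; the gap does.

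**Step 3: the low-glucose instruction**

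Duration = volume / rate = 500 ml / 25 ml/h = 20 h.

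Glucose content = 500 ml × 0.1 g/ml = 50 g, given at 25 × 0.1 = 2.5 g/h.

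Over the 3 h of visit 3: 25 × 3 = 75 ml, which is 7.5 g and 75/500 = 15% of the volume. Over 4 h: 100 ml, or 20%.

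The full volume at the stated rate does not fit a planned visit. The section does not say that the full volume must be given.

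**The case against.** Several counter-arguments carry weight.

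- **The gap depends on an unstated fact.** Every threshold is a whole number, and with whole-number readings there is no gap. This stands, so the gap must be stated conditionally. It does not touch the overlap at 12.
- **The overlap is one boundary value, with doses 2 IU apart.** True, and it limits the size of the point. The text still orders two doses for one reading.
- **The 20-hour infusion is not in the document.** The section gives a volume and a rate; 500 ml may simply be the bag to hang. Section 6.1.1 allows admission, and the visit length in section 11.0 describes planned visits, not a limit on treating an event. This stands. The infusion point is an unreconciled mismatch with the visit length, not a contradiction inside the rule.

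A reader might also infer stronger claims, which the documents do not support.

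- **That the rule cannot be applied safely.** The text shows that it cannot be applied uniformly; harm is an inference. With one department, any inconsistency would be between staff or visits, not between sites.
- **That readings in the affected ranges are likely**, particularly at the breath test, where "a substrate (80 g glucose dissolved in 300 ml of water) is swallowed". The protocol gives no glucose distribution.
- **That the primary endpoint is affected.** It counts grade 2 or higher adverse events in the first week after the first intervention (section 2.4.1). The breath tests at visits 3 and 6 fall before that week and about four weeks after the intervention. At visit 4 the capsules take 10 to 30 minutes and patients then go home, which leaves staff little time to use the table. Both arms follow the same rule under blinding, so no directional bias between arms is apparent.
- **That secondary endpoint 7 is affected.** It rests on patient-reported insulin use in a diary. Nothing shows that staff-given doses enter the diary, or that a 2 IU difference at one reading would matter.
- **That a separate version is needed for the breath-test day.** The section names the breath test and extends the trigger to the study itself. A separate version would be added clinical content, not the removal of a contradiction.

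**Conclusion.** The supplemental-insulin rule is internally inconsistent. At exactly 12 mmol/l it gives two doses, 4 IU and 6 IU, whatever the reading precision. Above 10 and below 11 mmol/l it triggers a regime with no instruction, assuming that glucose is read to a decimal. Nothing elsewhere in the protocol supplies the missing row or a tie rule, and the three rows are intact in the text, so a broken table does not explain it.

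The infusion point is secondary. It holds only if the full 500 ml is meant and the patient is not admitted; otherwise what is missing is a stated end point.

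No effect on the primary endpoint or on secondary endpoint 7 is shown. The size is that of a minor-to-moderate safety consistency correction. Confidence is high for the overlap, conditional for the gap, and lower for the infusion.

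**What to change.** In section 3.3.7 the sponsor should:

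1. Reconcile the trigger with the lower end of the first row, and state the precision to which glucose is read.
2. Make the rows contiguous and non-overlapping, so that each reading above the trigger maps to exactly one instruction.
3. Reconcile the infusion volume and rate with the visit length, say whether 500 ml is the bag size or the amount to be given, and state when the infusion ends.

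The thresholds, doses, volume and rate are for the sponsor's clinicians to set. This review proposes none.

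The cost is a protocol amendment of a few lines and a matching bedside instruction sheet. It needs no extra patients, visits or procedures.
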